11.0 DATA MONITORING COMMITTEE

The Data and Safety Monitoring Committee (DSMC) of the Winship Cancer Institute will provide oversight for the conduct of this study. The DSMC functions independently within Winship Cancer Institute to conduct internal monitoring functions to ensure that research being

Product: Siltuximab and Spartalizumab

Protocol/Version No.: 5, Date December 15, 2022

conducted by Winship Cancer Institute Investigators produces high-quality scientific data in a manner consistent with good clinical practice (GCP) and appropriate regulations that govern clinical research. Depending on the risk level of the protocol, the DSMC review may occur every 6 months or annually. For studies deemed High Risk, initial study monitoring will occur within 6 months from the date of the first subject accrued, with 2 of the first 5 subjects being reviewed. For studies deemed Moderate Risk, initial study monitoring will occur within 1 year from the date of the first subject accrued, with 2 of the first 5 subjects being reviewed. Subsequent monitoring will occur in routine intervals per the Winship Data and Safety Monitoring Plan (DSMP).

The DSMC will review pertinent aspects of the study to assess subject safety, compliance with the protocol, data collection, and risk-benefit ratio. Specifically, the Winship Cancer Institute Internal Monitors assigned to the DSMC may verify informed consent, eligibility, data entry, accuracy and availability of source documents, AEs/SAEs, and essential regulatory documents. Following the monitoring review, monitors will provide a preliminary report of monitoring findings to the PI and other pertinent individuals involved in the conduct of the study. The PI is required to address and respond to all the deficiencies noted in the preliminary report. Prior to the completion of the final summary report, monitors will discuss the preliminary report responses with the PI and other team members (when appropriate). A final monitoring summary report will then be prepared by the monitor. Final DSMC review will include the final monitoring summary report with corresponding PI response, submitted CAPA (when applicable), PI Summary statement, and available aggregate toxicity and safety data.

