This is a 3+3 standard phase I trial design. The plan is to evaluate two dose cohorts- 6 mg/Kg and 11 mg/Kg of siltuximab. An intermediate dose cohort (9 mg/Kg) will be evaluated only if we observe 2 or more DLT's in the 3 or 6 patients enrolled on the 11 mg/kg dose. If we observe 2 dose limiting toxicities on dose level 1, then the study will be completed with three patients (minimal number of patients). If we observe two DLT in the first three patients on dose level 1, the study will stop and the principal investigator will discuss at that point whether a lower dose level of siltuximab should be tested. If we do not observe any dose limiting toxicities the study will require 9 patients. If we observe one dose limiting toxicity per dose level (maximum number of patient), then the study would require 18 patients. Therefore the phase part sample size can range from 3 to 18 patients.

Expansion phase will be started once the recommended phase II dose (RP2D) is determined. Given minimal activity of checkpoint inhibitors in pancreatic cancer (Response rate less than 5%), an overall response rate of the combination of PD-1 plus IL-6 inhibitor of 20% would be considered clinically significant. With an alpha of 0.1, and power of 90% a total of 24 patients should be sufficient to make this determination. We will also obtain biologic endpoints with the paired biopsy samples that can help further develop the combination and understand its role in pancreatic cancers. We plan to enroll 24 patients on the RP2D level. Patients in the expansion phase will be assigned to treatment arms by PI (spartalizumab or spartalizumab plus siltuximab). After the first 3 weeks all patients will receive the combination therapy. There is no planned comparison between the two arms. The aim of the expansion phase is to confirm the safety profile and tolerability of the regimen in patients with pancreatic cancer.

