Early stopping for safety: If we observe more than 3 dose limiting toxicities as defined in Section 6.3.2 and Table 7 (excluding death since a single death will fulfil the stopping rule) during the first 8 weeks of treatment in the first 12 patients in the expansion cohort, study enrollment be halted pending a safety review by the safety monitoring committee for a single death. Consideration for lower dose regimen will be discussed with DSMC and sponsors. If the plan is to test additional dose levels, the protocol and informed consent will be amended and re-submitted for review by the IRB.

The total number of patients who will undergo treatment will range from 27 to 42 patients. In order to have 42 patients undergo treatment, we plan to enroll up to 70 patients to account for screen failures.

Product: Siltuximab and Spartalizumab

Protocol/Version No.: 5, Date December 15, 2022

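### The expansion's numeric DLT trigger covers only the first 12 of 24 patients; extending it is a cheap improvement

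*Combined protocol and SAP*

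**What the plan says.** Section 12.1 sets the expansion size: "We plan to enroll 24 patients on the RP2D level". It gives the purpose as: "The aim of the expansion phase is to confirm the safety profile and tolerability of the regimen in patients with pancreatic cancer".

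The early-stopping paragraph of the same section holds the only expansion-phase stopping rule. The trigger is "If we observe more than 3 dose limiting toxicities as defined in Section 6.3.2 and Table 7", counted over 8 weeks of treatment "in the first 12 patients in the expansion cohort". The action is "study enrollment be halted pending a safety review by the safety monitoring committee". A parenthesis adds a death clause: "excluding death since a single death will fulfil the stopping rule".

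Other places bear on the point. Section 2.0 defines the MTD by a DLT proportion below one-third in the first 6 weeks. The two-DLT rule in Section 6.2.2 applies to dose cohorts of six or fewer. Section 11.0 describes routine oversight: "Depending on the risk level of the protocol, the DSMC review may occur every 6 months or annually". It also describes study-team meetings that go through the toxicity logs, without a stated frequency or threshold.

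**The concern.** The sponsor judged that the expansion needed a numeric toxicity trigger, but wrote it for half the cohort and gave no reason for ending it at patient 12. If 3 of the first 12 patients have a DLT, no later count of non-fatal DLTs meets a pre-specified limit. In the extreme case, 3 of 12 followed by 12 of 12 (15 of 24, 62.5%) would not meet the DLT limb.

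This matters because the RP2D rests on 3 to 6 patients at that dose. With a true DLT rate p, a standard 3+3 cohort is cleared with probability (1−p)³ + 3p(1−p)²·(1−p)³. That is 43% at p = 1/3 and 31% at p = 40%. The expansion is where a dose cleared by chance should be noticed.

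**Working it through.** **Inputs.** Trigger of 4 or more DLTs in 12 patients and a cohort of 24 (Section 12.1); one-third limit (Section 2.0). The plan states no operating characteristics for the rule, so there is no figure of its own to reproduce. It gives no assumed DLT rate either, so I take 10% to 50% as a range. I count at most one DLT per patient and treat patients as independent.

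**Rule as written.** P(trigger) = P(X ≥ 4), X ~ Binomial(12, p). At p = 1/3 the probabilities of 0, 1, 2 and 3 DLTs are 0.0077, 0.0462, 0.1272 and 0.2120. They sum to 0.393, so the rule is silent 39.3% of the time and triggers 60.7% of the time. At p = 40% it is silent 22.5% of the time.

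**Carrying the same proportion forward.** 4/12 = 6/18 = 8/24 = 1/3. Among paths with 3 or fewer DLTs in the first 12, the added halt probability is the sum over x = 0 to 3 of P(X = x)·P(Y ≥ 6−x), with Y ~ Binomial(6, p). At p = 1/3, P(Y ≥ 6−x) is 0.0014, 0.0178, 0.1001 and 0.3196 for x = 0, 1, 2 and 3, so the sum is 0.081. Paths that also pass at 18 are then checked for 8 or more of 24.

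| True DLT rate | As written (4/12) | With 6/18 added | Any trigger, 8/24 review included |
|---|---|---|---|
| 10% | 2.6% | 2.7% | 2.8% |
| 20% | 20.5% | 23.4% | 24.6% |
| 30% | 50.7% | 58.1% | 62.1% |
| 33.3% | 60.7% | 68.8% | 73.3% |
| 40% | 77.5% | 85.1% | 89.1% |
| 50% | 92.7% | 96.8% | 98.4% |

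**Enrolments spared.** Suppose DLTs are known at once and enrollment pauses at the sixth patient with a DLT, at patient k (k ≤ 18). Then 24 − k enrolments are avoided, which averages about 0.6 at p = 1/3 over all trials. A single look at patient 18 would give 0.081 × 6, about 0.5. Reporting lag reduces this. If 27 to 42 treated patients accrue evenly over the estimated 12 months (an assumption), 27 × 8/52 = 4.2 to 42 × 8/52 = 6.5 patients enter in any 8 weeks. Most or all of patients 19 to 24 could therefore be enrolled before patient 18 completes the window.

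**The case against.** The strongest objection is that this is a design preference. The plan has an early check set at one-third, its analyses are descriptive (Section 12.2), and no section makes the MTD limit a running boundary for the expansion. That stands: a single early check is not an internal contradiction, and the point is an improvement rather than an error.

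A reader might infer that patients 13 to 24 are unmonitored, or that nothing that happens to them can prompt action. The documents do not support that. DSMC review continues and the committee may audit further. The study team reviews toxicity logs. SAEs are reported within 24 hours, and IND safety reports go out within 7 or 15 days. Unexpected grade 3 or higher events go to the sponsor immediately. The single-death clause may also reach the whole cohort: its sentence is garbled and its scope cannot be settled from the text. What remains is narrower. None of these is a DLT-rate trigger, and on either reading of the death clause non-fatal DLTs after patient 12 have no numeric limit.

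Two practical objections also stand. A limit at 24 patients cannot halt a cohort that is already fully enrolled. A limit at 18 spares few enrolments. Both shape the fix.

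**Conclusion.** The gap is real and modest. The plan pre-specifies a DLT trigger for 12 of 24 patients in a cohort whose aim is to confirm safety. At the protocol's own one-third limit that trigger stays silent 39% of the time (23% at a 40% rate), with no numeric check afterwards. Adding 6 of 18 raises the halt probability by about 8 points at both rates. With an 8-of-24 review included, the chance of any trigger is 73% and 89%.

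It would be tempting to read these gains as many patients protected, but the expected saving is about 0.6 enrolments at best. The benefit is that a possibly too-toxic dose is formally reviewed before the RP2D is confirmed. The figures rest on assumed DLT rates, independent patients, at most one DLT counted per patient and the same observation window at every look.

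**What to change.** Extend the early-stopping paragraph of Section 12.1:

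- After patient 12, pause enrollment for DSMC review as soon as the cumulative number of expansion patients with a DLT reaches 6 within the first 18, counting DLTs as they occur.
- Use one counting unit (patients with a DLT) and one observation window for all looks, including the existing one at 12.
- Treat 8 or more of 24 as a trigger for DSMC review of patients still on treatment and of the RP2D conclusion, not as an enrollment halt.
- State whether the single-death clause covers the first 12 patients or all 24.
- Reconcile the 8-week window and the citation of Section 6.3.2 with the DLT definition in Section 6.2.3 and Table 7, which uses the first 6 weeks.

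The cost is a short edit and some extra false pauses. At a 20% DLT rate these rise from 20.5% to 23.4%, or to 24.6% for any trigger including the 8-of-24 review. At a 10% rate the increase is about 0.2 points. The consequence each time is only a pause or a review.

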12.2 Statistical and Analytical Plans

Summary statistics will be presented for all safety, efficacy and biomarker parameter analyses. The purpose of these analyses is hypothesis generating and therefore, formal statistical testing will not be performed. Various exploratory statistical tests may be applied to data generated from this trial to generate hypotheses to be tested in subsequent trials. In general, data for continuous parameters will be presented using descriptive statistics including sample size, mean, and median; standard deviation; and minimum and maximum. Categorical parameters (such as pathologic response rate) will be displayed using counts and percentages. Toxicities will be presented as worst toxicity per patient and will be reported as percent toxicity.

12.3 Analysis Sets

All subjects who receive any amount of study drug will be included in the evaluation of safety and efficacy, except for patients who take less than 80% of their prescribed dose of siltuximab and spartalizumab since they will be considered in-evaluable for the primary endpoint of toxicity.

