6.2.3 Dose limiting toxicity (DLT)

A dose-limiting toxicity (DLT) is defined as an adverse event or abnormal laboratory value assessed as at least possibly related to study treatment that occurs within the first 6 weeks and meets any of the criteria included in Table 7. National Cancer Institute Common Terminology Criteria for Adverse events (NCI CTCAE) version 4.03 will be used for all grading.

The investigator must notify the Sponsor immediately of any unexpected CTCAE grade ≥ 3 adverse events or laboratory abnormalities. Prior to enrolling patients into a higher dose level, CTCAE grade ≥ 2 adverse events will be reviewed for all patients at the current dose level.

Table 7 Criteria for defining dose-limiting toxicities

Table / Criteria for defining dose mining toxicities					
DLT CRITERIA					
Thrombocytopenia Grade 3 with clinically significant bleeding					
Thrombocytopenia Grade 4					
Neutropenia Grade 4 lasting more than 8 days					
Febrile neutropenia CTCAE Grade ≥ 3					
Diarrhea CTCAE Grade $\geq 3 \geq 72$ hrs., despite the use of anti-diarrhea therapy					
Nausea/ vomiting CTCAE Grade \geq 3 \geq 72 hrs., despite the use of anti-emetic therapy					
• CTCAE Grade 2 pneumonitis if it persists > 7 days despite treatment with corticosteroids.					
• Second episode of grade 2 pneumonitis of any duration					
• Grade 3-4 pneumonitis of any duration					
• CTCAE Grade 3 immune-related toxicities that persist > 14 days with same severity despite treatment with corticosteroids.					
• Immune-related toxicities CTCAE Grade 4 of any duration					
Grade 3-4 infusion reaction					

Protocol/Version No.: 5, Date December 15, 2022

- Other non-hematologic treatment-related toxicity at Grade 3 or higher
- Any AE that leads to permanent discontinuation of siltuximab or spartalizumab
- Death
- 6.2.4 Dose expansion 24 patients will be treated on the dose expansion at the RP2D dose.
- 6.2.5 Duration of therapy: Subjects may withdraw consent at any time for any reason or be dropped from the trial at the discretion of the investigator should any untoward effect occur. In addition, a subject may be withdrawn by the investigator if enrollment into the trial is inappropriate, the trial plan is violated, or for administrative and/or other safety reasons. A subject must be discontinued from the trial for any of the following reasons:
 - The subject or legal representative (such as a parent or legal guardian) withdraws consent.

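### The only efficacy set in Section 12.3 spans all dose levels, whereas ORR was sized on 24 patients at the RP2D and no ORR set is named

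*Combined protocol and SAP*

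**What the plan says.** Section 12.3 (Analysis Sets) of the combined protocol and SAP is one sentence that serves both safety and efficacy. It opens with "All subjects who receive any amount of study drug will be included in the evaluation of safety and efficacy" and continues "except for patients who take less than 80% of their prescribed dose of siltuximab and spartalizumab". The reason it gives for the exception is that such patients cannot be evaluated for toxicity, the primary endpoint. It names no dose level, no cohort and no endpoint-specific set.

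Section 12.1 (Determination of Sample Size) deals with ORR in its paragraph on the expansion phase. It starts from a response rate below 5% for checkpoint inhibitors and states that "an overall response rate of the combination of PD-1 plus IL-6 inhibitor of 20% would be considered clinically significant". It then says "With an alpha of 0.1, and power of 90% a total of 24 patients should be sufficient to make this determination" and "We plan to enroll 24 patients on the RP2D level". Section 6.2.4 agrees: "24 patients will be treated on the dose expansion at the RP2D dose".

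The escalation part adds 3 to 18 patients, for 27 to 42 treated in all (Section 12.1). They receive siltuximab at 6 mg/kg, 11 mg/kg or, conditionally, 9 mg/kg (Section 6.2.1, Table 6). Table 4.0 lists ORR as the key secondary endpoint in patients given both drugs, again without a dose level or analysis set. Section 12.2 makes the analyses descriptive and hypothesis generating, without formal testing.

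**The concern.** The sample-size argument is about activity at one dose, the RP2D. The only efficacy set in the plan is about everyone who was dosed. No sentence connects the two.

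If Section 12.3 is followed literally, the reported ORR averages over siltuximab doses, including any that were tried and not selected. That average is not the rate at the RP2D, and it is not the quantity behind the choice of 24 patients.

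If Section 12.3 is not followed literally, the denominator has to be chosen later. The candidates are the 24 expansion patients, all patients at the RP2D, or all treated patients. The trial is open label (Section 6.3.5) and response is read locally (Section 14.3), so that choice could be made with the responses in view.

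The 80% exception adds a second problem. It removes patients according to exposure after baseline, for a reason that concerns toxicity, from a set that is also used for efficacy. Patients who stop or miss doses early may well differ in response from those who do not. The section also does not say over what period the prescribed dose is counted.

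**Working it through.** **Inputs.** From Section 12.1: 24 expansion patients at the RP2D, 3 to 18 escalation patients, 27 to 42 treated in total, null ORR below 5%, target ORR 20%, alpha 0.1, power 90%. From Sections 6.2.1 and 6.2.2: up to three dose levels of 3 to 6 patients each. Assumptions: a one-sided exact binomial test, because the plan states neither the test nor its sidedness; and, for the dilution check, an ORR of 5% at doses other than the RP2D, varied below.

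**The plan's own figure.** With a null rate of 5%, the smallest exact design with alpha at most 0.10 and power at least 90% at 20% needs 32 patients (at least 4 responses; alpha 0.074, power 0.907). With 24 patients and at least 3 responses, alpha is 0.116 and power 0.885. With at least 4 responses they are 0.030 and 0.736. A null rate of 3% to 4.4% would give an exact N of 25, close to 24. So 24 is not reproduced at 5%, but is nearly reproduced if the null rate is somewhat lower. This is a separate matter from the analysis set.

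**How far the two sets differ.** Treated patients: 24 + 3 = 27 up to 24 + 18 = 42. The largest escalation is three levels of 6. One of these is the RP2D, so at most 18 - 6 = 12 patients are at other doses. The figure of 27 corresponds to escalation ending after three patients, where Section 12.1 says the study stops. If both planned levels are completed with 3 patients each, the total is 24 + 3 + 3 = 30, of whom 3 are at another dose. All these counts are upper limits on the Section 12.3 set, because the 80% exception can only reduce them.

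**Dilution.** Pooled ORR = (n at RP2D × ORR at RP2D + n at other doses × ORR at other doses) / total. The count at the RP2D must include the 3 to 6 escalation patients treated at that dose. With 20% and 5%:

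- 27 at the RP2D, 3 at other doses: (27 × 0.20 + 3 × 0.05) / 30 = 5.55 / 30 = 18.5%
- 27 at the RP2D, 6 at other doses: (5.4 + 0.3) / 33 = 17.3%
- 30 at the RP2D, 12 at other doses: (6.0 + 0.6) / 42 = 15.7%
- 27 at the RP2D, 12 at other doses: (5.4 + 0.6) / 39 = 15.4%. This arises if two levels fill to 6 and the RP2D level needs only 3.

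**Range for the assumption.** If other doses respond at 0%, the pooled figure is 5.4 / 30 = 18.0% or 6.0 / 42 = 14.3%. If they respond at 20%, there is no dilution. If they respond better than the RP2D, the pooled rate is too high rather than too low. The documents give no response rate by dose, so the direction is not known.

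**Precision.** The exact 95% confidence interval for 5 of 24 responses (20.8%) runs from 7.1% to 42.2%.

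**The case against.** The strongest defence is that nothing has been specified wrongly. Section 12.3 is a general inclusion rule. It does not mention ORR, does not say that dose levels are pooled into one rate, and does not prevent tabulation by dose or cohort. Section 5.2 says that the expansion cohort will supply the preliminary response data, and Section 12.1 places the ORR reasoning there. ORR is a secondary endpoint described as preliminary (Section 3.2). The dilution, 20 - 18.5 = 1.5 to 20 - 15.7 = 4.3 points in the main cases, is small beside an interval of 7% to 42%. The expansion cohort is not uniform either, since some patients receive spartalizumab alone in cycle 1 (Sections 8.1.1.1 and 12.1).

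Most of this stands, and it limits the size of the point. It does not remove it. A descriptive percentage still needs a denominator, and the only one the plan defines for efficacy is not the one used to justify 24. Section 12.3 permits reporting by dose but does not require it.

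Two stronger readings are tempting. A reader might infer that every treated patient enters the efficacy evaluation; the 80% exception in the same sentence says otherwise. A reader might also infer that the planned ORR denominator is wrong; no sentence assigns a denominator to ORR, so the supportable finding is a mismatch and an omission.

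**Conclusion.** The point holds as a mismatch between two sections. The only efficacy set covers any dose level, subject to the 80% exception, while the ORR judgement was sized on 24 patients at the RP2D, and no ORR-specific set links them. Up to 12 of as many as 42 treated patients would be at other doses. Under the assumed 20% and 5% rates, the pooled ORR is about 18.5% to 15.7% (15.4% in the 39-patient case). That is a modest dilution, and it rests on a rate at other doses that the documents do not support or exclude.

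A reader might go further and infer an inflated false-positive rate, by carrying a fixed number of responders from 24 patients over to the larger set. The documents do not support that. They state no responder cut, and Section 12.2 rules out formal testing. A cut reset to the larger set would keep the error below 0.10: at least 4 of 30 gives 0.061 and at least 5 of 42 gives 0.057 at a 5% null rate.

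**What to change.** In Section 12.3:

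- Name the main ORR set as all treated expansion patients at the RP2D, reported with an exact confidence interval. Say that patients assigned to spartalizumab alone in cycle 1 are included.
- State that the 80% exposure exception does not remove patients from ORR, since its stated reason concerns toxicity.
- Report escalation patients separately by dose level.
- Show all patients treated at the RP2D, expansion plus escalation, as a labelled supportive analysis. This set could also be defended as the main one; what matters is that the choice is written down before responses are known.

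The cost is one paragraph and one table, with no change to enrolment or conduct. The change does not repair the sizing: with 24 patients and a null rate of 5%, requiring at least 3 responses still gives alpha 0.116 and power 0.885, which has to be dealt with separately in Section 12.1.
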